Study Protocol and Statistical Analysis Plan

Official Title of the Study: Anti-inflammatory Effect of Therapeutic Hypothermia in

Out-hospital Cardiac Arrest Patients with cardiogenic
Shock via Interleukin-6 Trans-signaling

NCT number: NCT02633358

[figure not shown]
[name]
China Medical University Hospital, Taichung, Taiwan
Date of the Document: August 25, 2018

Study Design and Patients

[figure not shown]
The clinical trial was designed to evaluate the effect of therapeutic hypothermia on IL-6 trans-signaling in patients with OHCA complicated with cardiogenic shock in comparison with placebo (ClinicalTrials.gov, NCT02633358). The study was conducted at the CMU hospital, Taichung, Taiwan from January 2015 to April 2018, and was approved by the institutional review board of the CMU hospital. All participants provided written informed consent through their surrogate decision-maker.

Patients with OHCA who were aged more than 18 years old were enrolled after resuscitation. The clinical definition of cardiogenic shock used was patients with cardiac problems who require vasopressors to maintain a mean arterial pressure of more than 65 mmHg after adequate fluid hydration and an initial lactate level of more than

18 mg/dL. The study design is outlined in the right figure.

[figure not shown]
Exclusion criteria were recovery from OHCA without cardiogenic shock, pregnancy, metastatic cancer, and family disapproval of patient participation in the clinical trial. A CONSORT flow diagram is displayed in the below table.

Therapeutic Hypothermia Protocol

The therapeutic hypothermia protocol was in accordance with that proposed by Scirica et al. (2013), with minor modifications (12). The first stage was rapid immediate cooling. The second stage was maintenance of a core temperature of 33°C–35°C for at least 24 hours (TTM34°C). The third stage was slow rewarming. The fourth stage was maintenance of normothermia to prevent fever. The therapeutic hypothermia protocol

is presented in the below figure.

Several cooling devices were selected freely, including Arctic Sun (Medivance Inc., Louisville, CO, USA) and Thermogard XP (Zoll Medical, Chelmsford, MA, USA) automatic core temperature control devices in addition to classical ice blankets.

Blood Sampling Protocol

Peripheral venous blood was drawn into blood collection tubes containing ethylenediamine-tetra acetic acid to prevent coagulation at 6 and 24 hours after resuscitation. To obtain plasma, these tubes were immediately placed on melting ice and centrifuged within 30 minutes using Centrifuge 5810R (Eppendorf AG, Hamburg, Germany) set at 4° C, $450 \times g$ for 25 minutes. Immediately following centrifugation, plasma was stored at -70° C in a freezer until further analyses.

IL-6 Trans-Signaling Immunoassay

The sandwich enzyme-linked immunosorbent assay was performed to measure IL-6, sIL-6R, Il-6/sIL-6R complex, and soluble glycoprotein 130 (sgp130) by using a human kit and standard protocol (R&D systems Inc., MN, USA). The absorbance of each well was determined using a SynergyTM H4 microplate reader at a 450-nm wavelength (BioTek instruments, Inc., VT, USA). Results were calculated using a 4-parameter logistic standard curve.

[figure not shown]
SOFA scores and Neurological Outcome

To evaluate the severity of organ failure, we used a SOFA score. This score reflected the severity of organ failure in cardiovascular system (mean arterial pressure), respiratory system (arterial pressure of oxygen divided by the fraction of inspired oxygen), central nervous system (Glasgow coma scale), liver (bilirubin), kidneys (creatinine), and coagulation (platelet).

| Variables | SOFA Score | | | | |
|---|----------------|--|------------------------------|--------------------------------------|---------------------------------------|
| | 0 | 1 | 2 | 3 | 4 |
| Respiratory Pao ₂ /Fio ₂ , mm Hg | >400 | ≤400 | ≤300 | ≤200† | ≤100† |
| Coagulation Platelets ×10 ³ /µL‡ | >150 | ≤150 | ≤100 | ≤50 | ≤20 |
| iver Bilirubin, mg/dL‡ | <1.2 | 1.2-1.9 | 2.0-5.9 | 6.0-11.9 | >12.0 |
| Cardiovascular Hypotension | No hypotension | Mean arterial pressure <70 mm Hg | Dop ≤5 or dob (any dose)§ | Dop >5, epi ≤0.1, or norepi ≤0.1§ | Dop >15, epi >0.1, or norepi >0.1§ |
| Central nervous system Glasgow Coma Score Scale | 15 | 13-14 | 10-12 | 6-9 | <6 |
| Renal Creatinine, mg/dL or urine output, mL/d | <1.2 | 1.2-1.9 | 2.0-3.4 | 3.5-4.9 or <500 | >5.0 or <200 |

Cerebral Performance Categories (CPC) scales of 1 (good recovery or slight disability) and 2 (moderate disability) were considered favorable neurological outcomes. CPC scales of 3 (severe disability) and 4 (comatose or persistent vegetative state) were considered poor neurological outcomes. A CPC scale of 5 (brain death) was considered as an indicator of mortality.

Cerebral Performance Categories Scale CPC Scale

Safar P. Resuscitation after Brain Ischemia, in Grenvik A and Safar P Eds. Brain Failure and Resuscitation, Churchill Livingstone, New York, 1981; 155-184.

Statistical Analysis

For assessing differences between the two groups, Student's *t*-test was used. For two time points between something before and after, paired *t*-test was used. Interaction effect, differences between the two groups and over time was analyzed by using multivariate analysis of variance (MANOVA) model. For categorical data, Chi-square test was used. Kaplan–Meier survival curves were compared between the two groups

by using the log-rank test. Risk ratios were reported as a measure of relative risk. A two-tailed *p* value of less than 0.05 was considered to indicate statistical significance.

All statistical analyses were performed using SPSS Statistics version 22.0 (IBM Corp., Armonk, NY, USA) and SAS 9.4 (SAS Institute, Cary, NC, USA).

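### The between-group t-test is named without an unequal-variance version; Welch's test would remove a conditional error in its p-value at almost no cost

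*Combined protocol and SAP*

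**What the plan says.** Everything on this point is in the Statistical Analysis section, read together with the sections on blood sampling and the immunoassay.

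- Group comparison: "For assessing differences between the two groups, Student's *t*-test was used". No variance assumption, variance check, transformation or unequal-variance version follows.
- Change within a group: "For two time points between something before and after, paired *t*-test was used". This does not compare the arms.
- Groups over time: "Interaction effect, differences between the two groups and over time was analyzed by using multivariate analysis of variance (MANOVA) model". This does compare the arms, so the t-test is not the only group comparison planned.
- Threshold: "A two-tailed *p* value of less than 0.05 was considered to indicate statistical significance".
- Outcomes: the immunoassay was used to "measure IL-6, sIL-6R, Il-6/sIL-6R complex, and soluble glycoprotein 130 (sgp130"), on blood drawn "to prevent coagulation at 6 and 24 hours after resuscitation". A SOFA score is also collected.

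The software is SPSS 22.0 and SAS 9.4; the t-test option is not stated. Arm sizes, allocation ratio and SDs are not in the readable text. The flow diagram that the plan refers to is not reproduced in the copy reviewed, which is not a fault of the plan.

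**The concern.** Student's t-test estimates one common variance from both arms. Its standard error is right if the arms have equal variance, and very nearly right if they have equal numbers. When both differ, it is too small if the smaller arm is the more variable (too many false positives) and too large if the larger arm is (lost power). Which of these applies cannot be known before the data are seen.

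Both conditions are plausible here, though neither is shown. Concentrations are positive, and a treatment that lowers their level often lowers their spread as well. The patients have cardiac arrest with cardiogenic shock, so some may die before the 24-hour draw, and the numbers analysed need not be equal even if the allocation was.

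There is also a practical gap. SPSS and SAS each print a pooled and an unequal-variance result, and the plan gives no explicit rule for which one to report.

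**Working it through.** The plan states no sample size, SD, effect size or allocation ratio, so there is no figure to reproduce. The only numeric input from the document is the two-sided 0.05 threshold. **Arm sizes and SD ratios below are assumptions.**

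**Large-sample formula.** Let the control arm have n₁ patients and SD s₁, and the cooled arm n₂ patients and SD s₂.

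- True variance of the difference in means: V_true = s₁²/n₁ + s₂²/n₂
- Variance that the pooled test uses: V_pooled = [(n₁s₁² + n₂s₂²)/(n₁ + n₂)] × (1/n₁ + 1/n₂)
- True type I error ≈ 2 × {1 − Φ(1.96 × √(V_pooled/V_true))}

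With control SD 1 and cooled SD 0.5:

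- 20/40: V_true = 1/20 + 0.25/40 = 0.05625. V_pooled = (30/60) × 0.075 = 0.0375. Ratio 0.667, critical value 1.96 × 0.816 = 1.60, error 11.0%.
- 40/20: V_true = 1/40 + 0.25/20 = 0.0375. V_pooled = (45/60) × 0.075 = 0.05625. Ratio 1.5, critical value 1.96 × 1.225 = 2.40, error 1.6%.
- 20/24: V_true = 1/20 + 0.25/24 = 0.0604. V_pooled = (26/44) × 0.0917 = 0.0542. Ratio 0.897, critical value 1.96 × 0.947 = 1.86, error 6.3%.

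**Simulation.** Normal data, equal true means, 100,000 trials per cell, rejection rate of the pooled test at nominal 5%:

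| Control/cooled | SD ratio 0.7 | SD ratio 0.5 |
|---|---|---|
| 20/20 | 5.1% | 5.3% |
| 18/20 | 5.6% | 5.9% |
| 20/24 | 5.7% | 6.5% |
| 20/30 | 6.8% | 8.4% |
| 20/40 | 8.0% | 11.2% |
| 30/20 | 3.8% | 2.8% |
| 40/20 | 2.8% | 1.8% |

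Repeat runs moved these cells by a few tenths of a percentage point at most; the 18/20 and 20/24 cells ranged over about 5.4% to 6.6%. Welch's test gave 4.8% to 5.2% in every cell. With equal SDs the pooled test is correct at any split (0.049 to 0.051 for splits from 30/30 to 15/45).

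**Cost of Welch's test when variances are equal.** With a true difference of 2.8 standard errors, power was 77.8% pooled against 77.7% Welch at 20/20, and 78.3% against 77.1% at 15/30. The loss is 0.1 and 1.2 points.

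**The MANOVA.** For one marker measured at two times in two groups, the group-by-time test is algebraically the pooled t-test on the 24-hour minus 6-hour change, and the group main effect is the pooled t-test on the average of the two times. A numerical check on unequal-variance data gave F = 1.1707, p = 0.28373 for the interaction, and the same values for the squared pooled t on the change. The group effect agreed likewise (F = 2.3046, p = 0.13442). These contrasts therefore carry the same equal-variance assumption.

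**The case against.** The strongest objection is that neither condition for harm is documented. Arm sizes and SDs cannot be read, and a missing figure is not evidence of imbalance. Loss of samples under equal allocation would usually give slight imbalance, where the error stays at about 5.4% to 6.6%; the figures above 8% need roughly a 2:1 split, or a halved SD at 2:3. This stands, and it is why the point is minor.

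A second objection is that the simulated case has an effect on spread with none on the mean. If cooling did nothing and the groups were otherwise comparable, the variances would be equal and the pooled test would hold its 5%. That also stands: the type I figures do not describe a treatment with no effect of any kind. Relatedly, if spread falls in proportion to level, a log scale would equalise the variances, so the problem depends partly on the scale chosen. For SOFA the documents give no specific reason to expect unequal spread.

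Third, the pooled form is inferred from the test's name. That is the conventional reading; if the sponsor meant otherwise, the same sentence of clarification is needed.

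Some stronger readings are tempting but unsupported. A reader might infer that every group comparison rests on the t-test, but a MANOVA is also planned for group differences. A reader might infer that confidence intervals are mis-sized, but the section describes none for a mean difference. A reader might infer that the main treatment contrast is affected, but the readable text names no primary outcome or primary test.

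**Conclusion.** The point holds in a limited form, as a minor one. The plan names a test whose p-value depends on equal variances unless the numbers analysed are equal, and offers no alternative. Under assumed SD ratios of 0.7 to 0.5 with equal means and normal data, the true error at nominal 5% runs from about 2% (40/20) through about 5% (equal arms) to about 11% (20/40). With equal numbers or equal SDs there is essentially no harm.

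A reader might infer that the trial's p-values are wrong. The documents do not support that, because they do not show that the arms differ in spread or in number analysed. The case for change rests on a better method being available at almost no cost.

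**What to change.** Replace the t-test sentence with one that names Welch's unequal-variance t-test for the between-group comparisons of the four concentrations and SOFA. This is the row for equal variances not assumed in SPSS and the Satterthwaite row in SAS. Apply it to all of these comparisons whatever the data look like, and do not choose between versions by a preliminary variance test.

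Beside the MANOVA, report Welch's test on the 24-hour minus 6-hour change for each marker. If the MANOVA was instead a joint test of several variables, Welch's test does not replace it, and its equal-covariance assumption should be stated.

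The cost is a sentence or two of wording and about 0 to 1 percentage point of power if variances are equal. No new data are needed. Because recruitment had ended by April 2018 and the document is dated August 2018 and written in the past tense, the practical step is to report the Welch result uniformly and say which version produced any p-value already reported.

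### IL-6 trans-signaling is tested through four analytes at two times, each at p<0.05, and the visible text sets no primary comparison, testing order or adjustment

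*Combined protocol and SAP*

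**What the plan says.** Study Design and Patients describes a trial "designed to evaluate the effect of therapeutic hypothermia on IL-6 trans-signaling in patients with OHCA" and cardiogenic shock. It gives the aim as that pathway, not as one variable.

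IL-6 Trans-Signaling Immunoassay says the assay was run to "measure IL-6, sIL-6R, Il-6/sIL-6R complex, and soluble glycoprotein 130 (sgp130"; that makes four analytes. Blood Sampling Protocol has blood drawn "at 6 and 24 hours after resuscitation".

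Statistical Analysis opens with "For assessing differences between the two groups" and names Student's t-test. It then names a paired t-test for an earlier against a later measurement, and a MANOVA for the interaction of group with time. One threshold covers everything: a two-tailed p "value of less than 0.05 was considered to indicate statistical significance".

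No visible sentence names a primary analyte, time point or contrast, sets an order of testing, or adjusts for the number of tests. None makes the MANOVA decisive, lists its dependent variables, or says whether it is run jointly or per analyte.

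**The concern.** Four analytes at two times give eight between-arm t-tests of the same question, before any interaction is tested. With each judged at 0.05, a claim about trans-signaling as a whole has no defined error rate. It depends on which results are allowed to carry the claim, and the text leaves that open.

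One joint interaction test as the sole basis would keep the error near 5%. Letting any significant analyte count would not. A reader who sees a single p<0.05 cannot tell which situation applies, and so cannot tell how much weight it bears.

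**Working it through.** **The plan's own figure.** There is none to reproduce. The visible text gives no sample size, power or overall error rate.

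**Inputs from the document.** Two-sided 0.05 per test (Statistical Analysis); four analytes (IL-6 Trans-Signaling Immunoassay); two times (Blood Sampling Protocol); between-arm t-tests and a group-by-time interaction (Statistical Analysis). Within-arm paired tests, SOFA, CPC and survival are left out because they are not between-arm tests of trans-signaling.

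**Assumptions, not in the document.** 20 or 30 patients per arm; within-patient correlation between 6 h and 24 h of 0.3 to 0.7; between-analyte correlation of 0 to 0.9; normal data; every patient sampled at both times. The last ignores deaths before 24 h.

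**Step 1: independent tests.** P(at least one false positive) = 1 - 0.95^k.
- k=1: 0.050
- k=4: 0.185
- k=8: 0.337
- k=12: 0.460. This value is not reached, because each 6-to-24 h change is a function of the two single-time values.

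**Step 2: correlated tests.** 20,000 simulated null trials were run per combination of assumptions. Student's t was used at each time, t on the change for a per-analyte interaction, and Hotelling's T-squared on the four changes for the joint interaction. The table gives the chance of at least one significant result in either direction.

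| Results that would count | Between-analyte correlation 0-0.8 | Correlation 0.9 |
|---|---|---|
| One joint interaction | 0.047-0.052 | 0.049-0.053 |
| Four 24 h t-tests | 0.112-0.189 | 0.093-0.096 |
| Four per-analyte interactions | 0.111-0.192 | 0.095-0.098 |
| Eight t-tests | 0.185-0.331 | 0.153-0.179 |
| Eight t-tests plus joint interaction | 0.219-0.343 | 0.188-0.209 |
| Eight t-tests plus four interactions | 0.258-0.411 | 0.216-0.220 |
| Four 24 h t-tests with Holm | 0.030-0.051 | 0.025-0.027 |

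**Step 3: cross-check of the twelve-test row.** A large-sample normal calculation at within-patient correlation 0.5 gives 0.1221 per analyte for the 6 h, 24 h and change contrasts together. Four independent analytes then give 1 - (1 - 0.1221)^4 = 0.406. With between-analyte correlation 0.5, 0.7 and 0.9 the figure falls to 0.344, 0.292 and 0.215. Adding a group main effect per analyte (0.1281 each) gives 1 - (1 - 0.1281)^4 = 0.422 for independent analytes.

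**Step 4: one direction only.** Suppose only one direction per analyte would support an anti-inflammatory claim; the plan states no directions. The chance, for between-analyte correlation 0-0.8, is then 0.058-0.100 (four 24 h t-tests), 0.094-0.179 (eight t-tests) and 0.140-0.244 (all twelve), against a nominal 0.025.

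**Step 5: price of Holm.** The strictest step is 0.05/4 = 0.0125, with critical value 2.498. For an analyte with 80% power at 0.05, the normal formula gives Phi(1.960 + 0.842 - 2.498) = Phi(0.304) = 0.62. Simulated t-tests give 0.60-0.61.

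**The case against.** **The plan never says one significant analyte is enough.** True, and this limits the point. The threshold sentence may be no more than a reporting convention. What is established is an undefined decision rule, not a demonstrated inflated error rate.

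**The MANOVA may be the intended main test.** It may, and run jointly it would hold about 5%. But the t-test is listed first, nothing ranks the two, and no dependent variables are given. A per-analyte MANOVA fits the wording equally well and carries about 10-19%. A reader might infer that the joint form is what the text means; the text does not decide it.

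**The paired-test sentence suggests that 6 h is a pre-treatment sample,** which would make the interaction the natural contrast. The hint is fair but not conclusive. That sentence names no variable or hour. Therapeutic Hypothermia Protocol says "The first stage was rapid immediate cooling" and gives no clock time, so cooling could already be acting at 6 h.

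**A primary outcome may be recorded elsewhere.** "The study design is outlined in the right figure", and that figure is not available here. The document also cites a registration that was not consulted. This stands: the point concerns the visible text and does not show that no primary outcome was ever chosen.

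**The study is mechanistic.** The title nonetheless announces an "Anti-inflammatory Effect of Therapeutic Hypothermia in" these patients. If exploratory results were intended, the plan should say so.

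**Conclusion.** The gap is real in the visible text and should be closed. If any one significant analyte result is read as an effect, the false-positive chance is about 9-19% for the four 24 h t-tests and about 15-33% for all eight, under the assumptions listed. Adding per-analyte interactions raises it further, to about 22% at between-analyte correlation 0.9. A single pre-named or joint test holds about 5%.

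A reader might infer that this trial carries a 41% false-positive risk. The document does not support that. The figure needs four uncorrelated analytes, twelve separate tests and a rule that any hit counts. One of the analytes is the complex of two others, which makes zero correlation among all four doubtful. Nor is 41% a ceiling, since a group main effect per analyte takes it to about 42%.

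A reader might also infer that the analysis was chosen after the results were known, because the document is dated 25 August 2018 and the study ran to April 2018. The dates allow this but do not show it.

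**What to change.** 1. If a primary analyte, time point and contrast were fixed before the data were seen, in a figure or in another prior record, name them. Test that comparison alone at two-sided 0.05.
2. Otherwise, state whether the 6 h sample is a pre-treatment value or an outcome time.
   - Outcome time: use the four between-arm comparisons at 24 h, with Holm at overall two-sided 0.05.
   - Pre-treatment value: use one joint group-by-time interaction over the four analytes at 0.05, or the four per-analyte interactions with Holm.
3. Report every other comparison as an estimate with a 95% confidence interval and no confirmatory claim.
4. If the choice was made after the data were seen, label the results exploratory. Holm or a joint test would then control error only nominally.

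**Cost.** Only wording and analysis change; no new data are needed. Under Holm, an analyte with 80% power at 0.05 keeps about 60-62% at the strictest step. The joint test carries no multiplicity penalty but does not identify which analyte differs. Its simulated power, for the same effect arising only after 6 h, runs from 41% to nearly 100% depending on the correlations, so it cannot be relied on without knowing them. An effect that is equal at 6 and 24 h produces no change between arms, so neither interaction option can detect it; the joint test rejects in about 5% of such trials. The role of the 6 h sample must therefore be settled first.
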